1. Screening visit and baseline data collection

Study participants will come from the patient rosters of study physicians. Patients who appear to be eligible after chart review and completion of standard of care test and procedures will be invited to undergo screening for the trial. Patients considered by the clinical center investigator as likely to be eligible for participation in the trial may be consented, registered and screened at a visit that is a part of the ongoing clinical care of the patient.

An open label pilot study to be conducted at Johns Hopkins Bayview Medical Center over 9 months to evaluate with nVNS for the symptomatic exacerbations of nauseas in patients with gastroparesis or CUNV. Approximately 30 patients will be enrolled in the study. Inclusion criteria will include patients 18 years or older with symptomatic nausea, vomiting and other symptoms suggestive of chronic nausea and vomiting of presumed gastric origin (Gastroparesis or CUNV). All the participants will come from the patient roster of the study physicians from the Division of Gastroenterology, Department of medicine: [name] (Principal Investigator), and [name].

In order to minimize the need for research-only in-person visits, telemedicine visits may be substituted for in person clinical trial visits or portions of clinical trial visits where determined to be appropriate and where determined by the investigator not to increase the participants risks. Prior to initiating telemedicine for study visits the study team will explain to the participant, what a telemedicine visit entails and confirm that the study participant is in agreement and able to proceed with this method. Telemedicine acknowledgement will be obtained in accordance with the Guidance for Use of Telemedicine in Research. In the event telemedicine is not deemed feasible, the study visit will proceed as an in-person visit. Telemedicine visits will be conducted using HIPAA compliant method approved by the Health System and within licensing restrictions

Revisions to the informed consent process are being permanently adopted for this research. Teleconsent will be used as opposed to in person consenting where possible to reduce unnecessary in person encounters specifically for a consent procedure. In the event teleconsent is utilized, participants will be provided with a copy of the Informed Consent prior to the teleconsent meeting either via email, fax, mail or previously provided during an in person visit.

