- State- Trait Anxiety Inventory (STAI)
- Average weekly frequency of migraine headaches for the last 4 week period
- COMPASS-31 score.

Anthropomorphic assessments (body weight, body height, body mass index [BMI]. Pregnancy test results that need to be recorded from chart review or obtained as part of the screening and EKG to rule out any abnormal baseline electrocardiogram such as second and third degree heart block, atrial fibrillation, atrial flutter, recent history of ventricular tachycardia or ventricular fibrillation, or clinically significant premature ventricular contraction, history of prolonged QT interval or a history of clinically significant arrhythmia.

Data will be captured on REDCAP and stored on the secure Hopkins server for this purpose.

2. Treatment Start Visit

At this visit, the patient will receive the gammaCore (nVNS) device and a video instruction will be use to explain how to properly handle the device. Treatment can only start after eligibility has been fully checked and all data collected at screening have been keyed into the trial database. Women of childbearing potential must have a negative urine pregnancy test.

After eligibility is confirmed with the clinical center staff the treatment can begin. The date of starting treatment is the start (ZERO) time for the timing of follow-up visits.

Frequency and duration of nVNS treatment.

The treatment will be self-administered using nVNS and will be applied for 8 weeks; 4 weeks will be used on one side of the neck and other 4 weeks in the contralateral side. A member of the study will provide the proper training on the correct use of nVNS. The patient will be instructed to use the nVNS in place of the rescue medications. When the nauseas gets bad enough that they feel to use a rescue medication they will first use the device on one side of the neck for two 2minute stimulations and wait fifteen minutes to check if the stimulation works. If this does not help either, they will stimulate with an additional 2 stimulations and wait for another fifteen minutes. If there is no improvement rescue medication will be used. nVNS can be used up to, but no more than, 8 times a day.

3. Follow-up Visits

Patients will return for follow-up visits at 4 and 10 weeks after treatment initiation. The specific

procedures to be completed at each of the follow-up visits are:

- Week 4 visit: The following questionnaires should be completed and collected:

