- Currently implanted with an electrical and/or neurostimulator device, including but not limited to cardiac pacemaker or defibrillator, vagal neurostimulator, deep brain stimulator, spinal stimulator, bone growth stimulator, or cochlear implant.
- History of carotid endarterectomy or vascular neck surgery on the right side.
- Implanted with metal cervical spine hardware or has a metallic implant near the gammaCore stimulation site.
- Any other condition, which in the opinion of the investigator would impede compliance or hinder the completion of the study.
- Failure to give informed consent.

6. **Drugs/ Substances/ Devices**

gammaCore Sapphire (nVNS) ²³⁻²⁵

Description:

nVNS is a multi-use, hand-held, rechargeable, portable device consisting of a rechargeable battery, signal-generating and -amplifying electronics, and a control button for the patient to control the signal amplitude. The device provides visible (display) and audible (beep) feedback on the device and stimulation status. A pair of stainless steel surfaces, which are the skin contact surfaces ("stimulation surfaces"), allow the delivery of a proprietary electrical signal. The patient applies electroCore-approved gel to the stimulation surfaces to maintain an uninterrupted conductive path from the stimulation surfaces to the skin on the neck. Tubes of electroCore-approved gel are provided with each unit and refill kit for this purpose. The stimulation surfaces are capped when not in use.

7. Study Statistics

Data analysis will be performed at Mayo Clinic Scottsdale, Arizona by [name], ([contact]). This site will no recruit participants.

Johns Hopkins will serve as coordinating center, responsible for overall data management, monitoring and communication among both sites, and general oversight of the conduct of this protocol.

Outcome measures

Primary: The primary outcome measure is the average daily use of rescue medications for exacerbation of nausea/vomiting.

Sample size justification

- Primary endpoint: Improvement in nausea control, as defined by a 50% reduction n the number of weekly doses of rescue medications, compared with baseline.

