- Total of 45 patients. This is a pilot study to assess the strength of the signal (improvement) with peripheral VNS for nausea. Since there is evidence that the left and right vagus may have different pathways within the CNS, with the left side being dominant in innervation of center involved in food aversion and nausea (Cell 175, 665–678, 2018), we are proposing to study three groups as follows
 - Group 1; Start with left sided stimulation 15 patients
 - Group 2. Start with right sided stimulation 15 patients
 - Group 3. Both sided stimulation 15 patients
- Our assumptions are as follows, in terms of the number of patients improving in each group

Group 1: 4/15 Group 2: 11/15 Group 3: 7/15

If these assumptions are true, the type I error will be < 0.05

8. Risks³²⁻³⁴

The adverse reactions observed in nVNS studies include:

- i. Shortness of breath (dyspnea), hoarseness, or change in voice during treatment.
- ii. Muscle twitching, discomfort, or pain during stimulation.
- iii. Change in taste (dysgeusia).

These first three reactions resolved after treatment was completed.

- iv. Local skin irritation/inflammation.
- v. Any progression of headache symptoms.

Adverse reactions not seen in the studies, but associated with implanted vagal nerve stimulation devices include:

- vi. Tingling, pricking, or a feeling of "pins and needles" on the skin where the device is applied (paresthesia or dysaesthesia) lasting beyond the treatment period.
- vii. Fainting (syncope), light-headedness, and/or dizziness.
- viii. Sweating.
- ix. Fatigue, depressed mood.
- x. Tinnitus.
- xi. Diarrhea.
- xii. Abnormal heart rhythm.

Adverse events will be evaluated in every follow-up visit. A form of Adverse Event will be completed if the candidate complains of any symptoms, sign, abnormal assessment or any combination of these. An adverse event can be expected side effect that is of a serious nature, or an unexpected side effect/event regardless of severity.

This study will monitor and report adverse events to ensure patient safety to IRB and FDA. Signs and symptoms associated with the adverse event will be graded as to severity by the clinical site staff as mild, moderate, or sever using Version 5.0 of the National Cancer Institute's Common Terminology Criteria for Adverse Events (CTCAE).

9. Benefits

Description of the probable benefits for the participant and for society.

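### The sample-size sentence ties type I error to assumed unequal response rates, and the 45 patients it supports conflict with the approximately 30 stated elsewhere

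*Combined protocol and SAP*

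**What the plan says.** In the combined protocol and SAP, the sample size justification in Section 7 (Study Statistics) plans 45 patients in three groups: "Group 1; Start with left sided stimulation 15 patients"; "Group 2. Start with right sided stimulation 15 patients"; "Group 3. Both sided stimulation 15 patients". The assumed numbers improving are "Group 1: 4/15 Group 2: 11/15 Group 3: 7/15". The conclusion drawn is "If these assumptions are true, the type I error will be < 0.05". The section describes the study as a pilot to gauge the strength of the signal and gives a left/right vagus rationale for having three groups. It names no test, contrast, sidedness, power, dropout allowance or period over which response is judged.

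Three other places bear on the same point:

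- Section 4, screening visit and baseline data collection: "Approximately 30 patients will be enrolled in the study". No groups are mentioned.
- Section 4, frequency and duration of treatment: "4 weeks will be used on one side of the neck and other 4 weeks in the contralateral side".
- Section 7, outcome measures: "The primary outcome measure is the average daily use of rescue medications for exacerbation of nausea/vomiting". The sample size justification then gives as primary endpoint a 50% fall from baseline in weekly rescue doses.

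**The concern.** Type I error is the probability of rejecting when the groups do not differ. The rates 4/15, 11/15 and 7/15 differ, so they describe an alternative hypothesis. A statement about type I error cannot be conditional on them. For a given sample size it is set by the test, its nominal level and the common response rate.

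This sentence is the only quantitative support for 15 per group. A reader may take it to mean that significance is assured if the assumptions hold, which it does not show. What is being sized is also unclear, because there are two enrolment totals, one group without a described procedure, two primary definitions and no response period.

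**Working it through.** **Inputs.** From Section 7: 15 per group and 4, 11 and 7 responders, so 22 of 45 in total. From Section 4: approximately 30 patients. Not in the documents, and assumed here: two-sided 0.05, independent groups, no dropout, and a Pearson chi-square or a Fisher-type exact test.

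**1. Reproducing the plan's figure as a p-value.** Treat the assumed counts as observed data.

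- Expected responders per group: 22/3 = 7.333. Expected non-responders: 23/3 = 7.667.
- Squared deviations: (4 − 7.333)² = 11.111; (11 − 7.333)² = 13.444; (7 − 7.333)² = 0.111. Sum = 24.667.
- Chi-square = 24.667 × (1/7.333 + 1/7.667) = 24.667 × 0.2668 = 6.581 on 2 df.
- With 2 df, p = exp(−6.581/2) = 0.037.
- Fisher-Freeman-Halton: each table (a, b, c) with a + b + c = 22 has probability C(15,a)·C(15,b)·C(15,c)/C(45,22). Summing over tables no more probable than (4, 11, 7) gives p = 0.046.
- Left against right only (4/15 against 11/15): Fisher p = 0.027.

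All three are below 0.05, so the stated figure is reproduced if it is read as a p-value.

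**2. Type I error.** Set all three rates to a common value r and sum the binomial probabilities of every outcome with p < 0.05. The result depends on r and on the test:

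| Common rate r | Chi-square | Fisher-Freeman-Halton |
|---|---|---|
| 0.30 | 0.0523 | 0.0401 |
| 0.40 | 0.0505 | 0.0425 |
| 22/45 | 0.0504 | 0.0442 |
| 0.60 | 0.0505 | 0.0425 |

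The unequal rates 4/15, 11/15 and 7/15 do not enter this calculation.

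**3. What those rates do determine: power.** Power = Σ Bin(a; 15, 4/15) · Bin(b; 15, 11/15) · Bin(c; 15, 7/15) over all (a, b, c) with p < 0.05.

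| Comparison | Test | Power |
|---|---|---|
| Three groups of 15 | Chi-square | 0.656 |
| Three groups of 15 | Fisher-Freeman-Halton | 0.635 |
| Left vs right, 15 each | Fisher | 0.596 |
| Left vs right, 15 each | Uncorrected chi-square | 0.744 |
| Three groups of 10 (assumed split of 30) | Chi-square | 0.433 |

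If the sponsor's assumptions are exactly right, the three-group chi-square still misses significance in about 1 − 0.656 = 34% of trials.

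**4. Size and structure.** 45 − 30 = 15 patients, an increase of 15/30 = 50% over the Section 4 figure. The word approximately does not cover that, and nothing describes the 30 as completers or as a subset. Thirty would equal two groups of 15, but the documents do not say so.

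The four-week change of side in Section 4 fits Groups 1 and 2, which are defined by starting side. It provides nothing for Group 3. If the change of side applies, patients in Groups 1 and 2 have used both sides by week 8. The unnamed response period then decides whether 4/15 against 11/15 compares sides or orders.

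**5. Precision, as the alternative basis.** For illustration, at the pooled rate 22/45 = 0.489, the normal-approximation 95% half-width is 1.96 × √(0.489 × 0.511/n). This is 0.146 for n = 45, 0.179 for n = 30, and 0.253 for a single group of 15.

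**The case against.** The strongest reply is that this is an open-label pilot, that such a study may choose its size without a power calculation, and that the sentence is loose wording for a p-value below 0.05. The first part stands: low power is not a defect here. The second does not rescue the sentence, because a p-value computed from the expected counts does not state the chance of success, and 45 against approximately 30 remains.

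A second reply is that a between-group power figure would not match the aim. Section 2 asks whether treatment reduces rescue medication use, and the Section 7 endpoint is change from baseline. Both are within-patient questions. This stands, and the fix therefore offers precision as an alternative to power.

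A third reply is that average daily use and a halving of weekly doses can both come from the same rescue diary. That is fair: a measure and a cut-off on it are not strictly contradictory. But both are labelled primary, and the assumed counts fit only the second.

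A reader might go further and infer that type I error exceeds 0.05. The documents do not support this, because no test is named. With the Pearson chi-square the actual size passes 5% slightly at some common rates (at most 5.23%). With Fisher-Freeman-Halton it stays at or below about 4.4%.

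**Conclusion.** The point holds. The sentence attributes to the assumed rates a property that they cannot determine, and the number of patients it supports conflicts with Section 4 by 15. Those two findings rest on the documents alone.

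That the figure is a p-value is an inference from its matching three plausible tests. The power of about 66% (chi-square) or 63% (Fisher-Freeman-Halton) assumes that the stated rates are true, three independent groups of 15, two-sided 0.05 and no dropout. The 43% figure also assumes that 30 patients would be split 3 × 10.

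A reader might infer that the trial is too small and should enrol more. The documents set no power target and describe a pilot, so that does not follow. The need to correct the plan rests on the false property and on the unresolved N and group structure, not on the level of power.

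**What to change.** 1. Delete the type I error sentence from Section 7.
2. Reconcile the enrolment and treatment text in Section 4 with Section 7, so that there is one N and one group structure, and say how Group 3 relates to the side schedule. The choice of stimulation schedule is the sponsor's and is not addressed here.
3. State which of the two Section 7 definitions is primary, and over which period response is assessed.
4. Justify the size in one of two ways:
   - Present N as a pilot choice and give the precision of the responder rate, which matches the within-patient objective in Section 2.
   - If the three-group comparison is kept, name the test and give its power. Possible wording: Pearson chi-square (2 df) across three groups of 15, two-sided 0.05, no dropout, response assessed over [period to be named]; about 66% power if the true rates are 4/15, 11/15 and 7/15. With Fisher-Freeman-Halton the figure is 63%. Recompute if N, groups, endpoint or evaluable numbers change.

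The cost is protocol wording plus sponsor decisions on N, groups, primary definition and response period. Keeping 45 means 15 more patients than Section 4 states, within the same 9-month recruitment. Keeping about 30 means redoing the Section 7 calculation. If power is reported, the stated figure will look less favourable than the present one. Neither route requires a larger trial than Section 7 already describes.
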